It will have to decide on the continuation of the study in light of the safety data. The sponsor may refer to it at any time in the event of significant events concerning the safety of the treatment. An analysis of SAEs is planned after the inclusion and intra-arterial treatment of the first 10 patients.

XII.6 Imaging Review Committee/Radiologist Panel

The anonymized copies of the evaluation reports will be centralized at the CRGA on the 'FFCD Images' platform using a secure transmission via the company ETIAM.

The RECIST version 1.1 and EASL responses will be reviewed by this panel of independent radiologists at a later date, who will confirm the responses and dates of tumor progression or recurrence once all study examinations have been retrieved.

XII.7 Steering Committee

A Steering Committee will be set up. It will be chaired by the study coordinator, [name] [name]. This committee will also include the president of the FFCD, the statistician of the FFCD and the president of the Biological Research Committee (if applicable). Its mission will be, among others, to take decisions related to the management of the research (amendment, premature closure if necessary, ...).

XII.8 14.2 Biological Research Committee

If it is decided to set up the collection of surgical parts relating to secondary hepatic resections, a Biological Research Committee will be established. Its mission will be to deal with problems related to the collection and banking of specimens and the organization of their analysis. The committee shall meet regularly and report its proposals to the Board of Directors. This committee will include the study coordinator and a biologist; the chairperson of this committee will be designated afterwards.

XIII. JUSTIFICATION OF THE TEST

The treatment of metastatic colorectal cancer has become more diverse in recent years. Several chemotherapy regimens and targeted therapies are available as first-line treatment. The majority of liver metastases are not immediately resectable (in about 85% of patients) and studies with different combinations indicate that aggressive first-line chemotherapy in initially inoperable patients can achieve complete resection of metastatic disease (1). It is therefore important to develop new therapeutic strategies in metastatic colorectal cancer.

Anti-tumor therapy

Intravenous triple therapy combining 5FU, oxaliplatin, and irinotecan has been evaluated in randomized trials (Falcone et al, (2); Souglakos et al, (3)). They showed good response rates (43-60% according to RECIST criteria), progression-free survival (about 62% at 9 months), secondary resection rates of liver metastases and overall survival. Tolerability was acceptable if the WHO performance status at inclusion was <2, bilirubinemia <1.5 times LNS, and primary neutropenia prophylaxis (G-CSF) was administered. These trials suggest that the combined use of 5FU, oxaliplatin, and irinotecan is an option in the treatment of first-line metastatic colorectal cancer.

Intra-arterial chemotherapy

It has been shown in numerous trials over the past 20 years that intra-arterial chemotherapy can improve response rates and overall survival, particularly in patients with liver-limited metastatic disease. In patients with liver-limited metastases, locoregional chemotherapy exposes liver tumor cells to high concentrations with minimal systemic toxicity. However, FUDR and, more recently, oxaliplatin have been the most extensively tested drugs by this route, with high response and secondary resection rates of liver metastases (4-7), but no large phase III is currently available to validate their use in daily practice. In addition, there is a clear lack of standardization of the therapeutic protocol for IA injection and the use of intra-arterial devices is still limited to very specialized centers.

Advantages of the DEBIRI

An intra-arterial hepatic chemotherapy protocol with irinotecan-loaded microbeads (DEBIRI) has recently been developed. Preliminary results are promising. A phase II study of 82 patients with unresectable liver metastases, after failure of two lines of chemotherapy, treated with DEBIRI achieved a 78% response rate and improved quality of life in 90% of patients (8). Acute toxicity is common (post-embolism syndrome in 80% of cases) but easily manageable.

This treatment was also tested in another second- or higher-line study in 55 patients with colorectal cancer with unresectable liver metastases (9). Results showed a 75% response rate at 1 year and a median overall survival of 19 months. This treatment also appeared to be well tolerated, with 28% grade 1-3 toxicities. It did not appear to be more toxic in combination with systemic chemotherapy (continuous IV or oral 5FU, n = 16) than alone.

More recently, a randomized phase III study in the same population (colorectal cancer with liver metastases after at least 2 lines of treatment) compared FOLFIRI to DEBIRI (10). Results were encouraging with response rates of 68.6% in the experimental arm versus 20% in the control arm. Quality of life, median overall survival and progression-free survival were also improved in the experimental arm. Tolerance showed more acute toxicities (grade 2-3) in the experimental arm and more late toxicities (grade 2-3) in the control arm. Finally, healthcare costs were reduced in the experimental arm.

Finally, DEBIRI was combined with FOLFOX in a 1^{ère} metastatic line of treatment for patients with metastatic colon cancer in a phase I study of 10 patients. Response rates at 9 and 12 months were 100%, with 40% secondary resection or removal of metastases. The combination was well tolerated with only one grade 3 event (hypertension).

Objectives

The objective of this study is to evaluate the feasibility, safety, and efficacy of chemotherapy combining conventional systemic FOLFOX with DEBIRI intra-arterially in the liver as first-line therapy in patients with CRC with predominantly hepatic metastases in a multicenter, single-arm phase II trial.

XIV. REFERENCES

- 1 **Pozzo C**, Basso M, Cassano A, et al: Neoadjuvant treatment of unresectable liver disease with irinotecan and 5-fluorouracil plus folinic acid in colorectal cancer patients. Ann Oncol 15:933-939, 2004
- 2 **Falcone A**, Ricci S, Brunetti I, et al: Phase III trial of infusional fluorouracil, leucovorin, oxaliplatin, and irinotecan (FOLFOXIRI) compared with infusional fluorouracil, leucovorin, and irinotecan (FOLFIRI) as first-line treatment for metastatic colorectal cancer: the Gruppo Oncologico Nord Ovest. J Clin Oncol. 2007 May 1;25(13):1670-6
- 3 **Souglakos J**, Androulakis N, Syrigos K, et al: FOLFOXIRI (folinic acid, 5-fluorouracil, oxaliplatin and irinotecan) vs FOLFIRI (folinic acid, 5-fluorouracil and irinotecan) as first-line treatment in metastatic colorectal cancer (MCC): a multicentre randomised phase III trial

from the Hellenic Oncology Research Group (HORG). *Br J Cancer*. 2006 Mar 27;94(6):798-805

4 **Boige V**, Malka D, Elias D, et al: Hepatic arterial infusion of oxaliplatin and intravenous LV5FU2 in unresectable liver metastases from colorectal cancer after systemic chemotherapy failure. *Ann Surg Oncol*. 2008 Jan;15(1):219-26

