Date:  Signature:

STAMP of the CENTER :

Send the original to CRGA de la FFCD - [name]

SYNOPSIS

Essay title:	Trial FFCD-1201: INTRA ARTERIAL IRINOTECAN (DEBIRI) LOADED MICROBALLS IN COMBINATION WITH FOLFOX SYSTEMIC CHEMICAL THERAPY IN COLORECTAL CANCER PATIENTS WITH NON-RESCURABLE HEPATIC METASTASIS - NON RANDOMIZED MULTICENTRIC PHASE II
Trial number	FFCD- 1201
Developer	FFCD
Coordinator(s)	Pr. [name], [name]
Rationale for the study	
The treatment of patients with colorectal cancer with liver metastases is currently based on systemic chemotherapy.
 
Triple therapy combining 5FU, oxaliplatin and irinotecan by IV route has been shown to be effective in terms of response and secondary resectability, however it is particularly toxic.
 
Intra-arterial hepatic chemotherapy (IHC) has been studied in several studies. It has shown good efficacy with oxaliplatin and FUDR. However, it is a difficult procedure to implement and is reserved for expert centers.
 
The aim of this protocol is to use triple therapy with 5FU, oxaliplatin, and irinotecan, the latter delivered intra-arterially to the liver, loaded on microbeads (DEBIRI). Moreover, the DEBIRI chemoembolization procedure is limited to 2 sessions for each lobe, and could be more easily generalized.

Objectives	
Principal:
 
Progression-free survival rate at 9 months according to RECIST 1.1.
 
Secondary:
 
Tolerance to treatment
 
Response rate according to RECIST 1.1 criteria at 9 months
 
Response rate according to EASL criteria at 9 months
 
Hepatic progression-free survival according to RECIST 1.1
 
Overall survival
 
Progression-free survival
 
Secondary resection rate
 
Evolution of tumor marker levels

Inclusion criteria	
 - Histologically proven colorectal adenocarcinoma, - Radiologically or histologically proven liver metastases - At least one measurable liver lesion according to RECIST v1.1 criteria - Age \geq 18 years

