Study design and treatment plan	
Microbeads (100-300μm), loaded with irinotecan (DEBIRI). The maximum dose per procedure is 100 mg of irinotecan, combined with intravenous FOLFOX.
 
For patients with unilobar or bilobar liver involvement, DEBIRI will be injected at D17 and D45 (after the 2nd and 4th cycle of systemic chemotherapy with FOLFOX).
 
Patients with bilobar involvement but for whom the investigator decides that the treatment will be unilobar and sequential, there will be 4 sessions. Thus, the right and left livers will be treated alternately. The DEBIRI administrations will then be performed at D17, D31, D45, D59, or in case of a shift in chemotherapy treatment, after the 2^{ème}, 3^{ème}, 4^{ème} and 5^{ème} cycle of FOLFOX.
 
FOLFOX will be administered every 2 weeks until progression or unacceptable toxicity.

Statistical methods	
A 1-step Fleming design will be used, with a one-sided α risk of 5% and a power (1-β) of 90%.
 
The assumptions are:
 
 • H0: A proportion of patients living without progression of 55% during the first 9 months is uninteresting; • H1: A proportion of patients living without progression of more than 55% during the first 9 months would show the interest of the treatment; a proportion of 75% is hoped for.

	
Total number: 48 evaluable patients
 
Taking into account a 20% rate of lost to follow-up or non-evaluable patients, 58 patients should be included.
 
At the end of recruitment:
 
During analysis:
 
 - if 32 or fewer patients are alive without progression, then the treatment is considered ineffective - if 33 or more patients are alive without progression, then the treatment is considered effective 
The decision rule will be adjusted based on the actual number of evaluable patients.

Number of subjects needed	58
Associated translational studies	
 - On lipid parameters: The objective of this study will be to evaluate the impact of the different parameters of the lipid profile and the metabolism of lipoproteins on the response to treatment. - On Pathology: At the end of the study, if a sufficient number of patients have undergone secondary resections of liver metastases, a collection of surgical parts will be organized. An anatomopathological study of the tumor parenchyma and the healthy parenchyma resected after DEBIRI treatment will be performed.

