The patient's inclusion will be done directly via the eCRF; the inclusion confirmation and the inclusion number will be sent to you by email. For any help, the FFCD Randomization - Management - Analysis Center in Dijon is open from Monday to Friday from 9:00 am to 6:00 pm.

After inclusion in the study, treatment should begin within a maximum of 2 weeks.

V. TREATMENT

[figure not shown]
V.1 Treatment scheme:

Bilobar treatment in 2 sessions:

Following this initial treatment plan, all patients will receive FOLFOX chemotherapy every 2 weeks according to the usual schedule until progression or unacceptable toxicity.

Sequential unilobar treatment in 4 sessions:

The chemoembolization treatment can, at the investigator's choice, be administered in a unilobar and sequential manner, in 4 sessions. Thus, the right and left livers will be treated alternately. The administrations of DEBIRI will then be performed at D17, D31, D45, D59 (+/- 2 days), or in case of delayed chemotherapy treatment, 3 days (+/- 2 days) after C2, C3, C4 and C5 of FOLFOX. After this initial treatment plan, all patients will receive FOLFOX chemotherapy every 2 weeks according to the usual schedule until progression or unacceptable toxicity.

V.2 Chemoembolization

V.2.1 Scheduled irinotecan dose

Each vial of DC Bead is loaded with 100 mg of irinotecan. It is intended to use the contents of one vial per lobe. For unilobar disease, there will be 1 vial loaded with 100 mg of irinotecan and for bilobar disease, 2 vials loaded with 200 mg, if the treatment is done in one session.

V.2.2 Microbead size

Microbeads with a size of 100-300 μ m will be used in this study and provided by the sponsor.

V.2.3 Precautions and instructions for loading the medication:

Instructions for loading the beads will be provided in the investigator's binder and the pharmacy bag.

V.2.4 Dilution of the loaded microbeads with a contrast agent

Remove the excess supernatant of the irinotecan solution from the vial containing the loaded microbeads before mixing with the contrast agent. A non-ionic contrast agent should be used. It is recommended that the microbeads be diluted prior to injection with a volume of at least 5-10 mL of contrast agent per mL of microbeads (i.e., 10-20 mL of contrast per vial of microbeads). A good suspension of the microbeads in the contrast must be obtained before administration.

V.2.5 Conservation of loaded microbeads:

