Irinotecan-loaded microbeads can be stored for up to 24 hours in a refrigerator at 2°C to 8°C or for up to 4 hours at room temperature, with or without a non-ionic contrast agent.

V.2.6 Pre-administration assessment:

Prior to each chemoembolization procedure, the patient should be ensured to have adequate liver and hematologic function (total bilirubin \leq 1.5N, ALT, ASAT, and PAL \leq 5N, albumin \geq 2.5g/dL; PNN \geq 1500/mm³, platelets \geq 100,000/mm³, INR $<$ 1.5) and a patent portal trunk.

V.2.7 Procedure

The DEBIRI procedure will begin with a 4 or 5Fr peripheral arterial approach at the operator's convenience.

The operator will first proceed to a diagnostic phase. Successively, he will catheterize the superior mesenteric artery and the celiac trunk. During these angiographies, the operator will identify the disposition of the hepatic arterial vascularization, the permeability of the portal trunk and the vascular topography of the lesions. The operator may be required to perform selective angiography of the phrenic, inferior epigastric, and internal mammary arteries when peripheral hepatic tumors have been identified.

After this diagnostic phase, **lobar administration** will be used whenever possible. The operator will catheterize the right and left hepatic arteries with a maximum 3Fr microcatheter. Prior to DEBIRI injection, the operator will place the microcatheter on the right downstream of the cystic artery, and on the left downstream of the right gastric artery. The right gastric artery may be prophylactically embolized if the operator deems it necessary.

Each vial of irinotecan-loaded microbeads (DEBIRI) will be mixed with at least 10-20 mL of non-ionic iodinated contrast medium (e.g. Imeron 350, Omnipaque 350).

The goal of the procedure is to deliver the entire dose of irinotecan. It is important to maintain anterograde flow in the vessel during the procedure.

DEBIRI should be injected slowly, at a rate of 1 mL of solution per minute.

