When the near stasis point is observed prior to the full dose of irinotecan, the injection of DEBIRI is discontinued regardless of the volume of beads delivered at that time. Therefore, some patients may not receive the entire contents of the prepared vial and may receive a total dose of less than 100 or 200 mg, respectively, in cases of lobar or bilobar involvement. The operator will make sure to respect these recommendations to prevent an inappropriate reflux of DEBIRI that would cause ischemia or necrosis of non-targeted territories.

When the planned dose of irinotecan is administered before the near-stasis point is reached, no additional embolization should be performed with products such as gelfoam, lipiodol or microspheres.

The operator will take care to avoid sedimentation of the beads in the syringe during the procedure by performing gentle rotations or using a three-way valve to keep the beads suspended in the solution.

Extrahepatic vessels may be embolized prophylactically, at the discretion of the interventional radiologist, to minimize extrahepatic infusion of irinotecan beads.

For multifocal or bilobar disease, embolization of each lobe will be performed, at the investigator's discretion, either during the same session or in a unilobar and sequential manner, in 2 sessions. If the treatment is done in one session, the catheter will be placed in the

right and then left hepatic artery and a maximum of one vial of DEBIRI will be administered in each lobe.

Catheter removal and hemostasis at the puncture site will be accomplished by manual compression or by placement of a percutaneous puncture site closure device (e.g., Angioseal™).

Patients will need to be hospitalized overnight following the procedure. After the chemoembolization procedure, vital signs, femoral access point, pain management and hydration will be observed in all patients.

The amount of contrast material delivered to the patient during the procedure, the radiation dose, and the fluoroscopy exposure time should be recorded. The embolized vessels and the amount of embolic agent will be recorded.

All treatments used during the procedure, including analgesic treatments, should be recorded. Any unused irinotecan-loaded microbeads will be discarded.

V.2.8 Peri-chemoembolization treatment recommendations/pre-medication for chemoembolization:

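### The synopsis caps irinotecan at 100 mg per procedure, while Protocol V.2.1 and V.2.7 allow up to 200 mg when both lobes are treated in one session

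*Protocol*

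**What the plan says.** The synopsis, under the study design and treatment plan, gives a ceiling for the intra-arterial component: "The maximum dose per procedure is 100 mg of irinotecan, combined with intravenous FOLFOX". The next sentence covers patients with unilobar or bilobar involvement together and says that "DEBIRI will be injected at D17 and D45". The four-session sequential option for bilobar disease follows as a separate case. This part of the synopsis mentions neither a vial per lobe nor 200 mg.

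The body of the protocol is more detailed. V.2.1 sets 100 mg of irinotecan per vial and adds: "It is intended to use the contents of one vial per lobe". Unilobar disease therefore has one vial and, "for bilobar disease, 2 vials loaded with 200 mg, if the treatment is done in one session". V.2.7 agrees. In a one-session bilobar treatment, the right and then the left hepatic artery are catheterised and each lobe may receive up to one vial. The same section gives 100 mg and 200 mg as the full doses for lobar and bilobar involvement when it explains that some patients will receive less.

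**The concern.** A bilobar patient treated in one session has two different maxima, depending on which part of the protocol is read. An operator who follows V.2.1 and V.2.7 and delivers more than 100 mg in total exceeds a maximum written in the synopsis of the same protocol.

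This is the dose ceiling of the investigational component, so it bears on patient safety and on what would count as a protocol deviation. The affected case is also an ordinary one: V.2.7 leaves the choice between one-session and sequential treatment to the investigator.

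**Working it through.** **Inputs**

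- Synopsis maximum: 100 mg per procedure.
- V.2.1: 100 mg per vial, and one vial per lobe.
- V.2.1 and V.2.7: up to two vials when both lobes are treated in one session.
- Synopsis: sessions at D17 and D45 in the two-session scheme.
- Synopsis and V.1: four sessions in the sequential scheme.

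**Arithmetic**

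Dose per session = 100 mg per vial × one vial per lobe × number of lobes treated. With two lobes this reproduces V.2.1's own figure of 200 mg.

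| Treatment | Per session, V.2.1 and V.2.7 | Synopsis maximum | All sessions, V.2.1 and V.2.7 | Synopsis maximum × sessions |
|---|---|---|---|---|
| One lobe, 2 sessions | 1 × 100 = 100 mg | 100 mg | 2 × 100 = 200 mg | 2 × 100 = 200 mg |
| Both lobes, 2 sessions | 2 × 100 = 200 mg | 100 mg | 2 × 200 = 400 mg | 2 × 100 = 200 mg |
| Sequential, 4 sessions | 1 × 100 = 100 mg | 100 mg | 4 × 100 = 400 mg | 4 × 100 = 400 mg |

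Only the second row conflicts. There the ratio is 200 / 100 = 2.0. The texts part company once the delivered share of the prepared dose exceeds 100 / 200 = 50%. The largest excess over the synopsis maximum is 200 − 100 = 100 mg per session, or 400 − 200 = 200 mg over D17 and D45. The two-session totals are simply the per-session contrast counted twice; the documents set no cumulative ceiling.

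**What *procedure* means**

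The conflict depends on reading *procedure* as the whole session, so the protocol's usage has to be checked.

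- V.2.7 is headed as the procedure and starts with vascular access: "The DEBIRI procedure will begin with a 4 or 5Fr peripheral arterial approach". It continues through diagnostic angiography, treatment of one or both lobes, catheter removal and an overnight stay after the procedure.
- V.2.7 asks for contrast volume, radiation dose and fluoroscopy time during the procedure, with no split by lobe.
- V.2.6 says: "Prior to each chemoembolization procedure, the patient should be ensured to have adequate liver and hematologic function". Section VII ties the matching clinical and laboratory work-up to each session.
- The synopsis rationale says that "the DEBIRI chemoembolization procedure is limited to 2 sessions for each lobe". Here the word denotes the technique, which gives the 100 mg limit no per-lobe meaning.

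**Near-stasis**

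V.2.7 provides that, if near-stasis comes before the full dose, "the injection of DEBIRI is discontinued regardless of the volume of beads delivered at that time". A bilobar patient stopped at or below 100 mg in total breaches neither text. This narrows the conflict but does not remove it, because V.2.7 makes delivery of the entire dose the goal.

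**The case against.** The strongest reply is that *procedure* in the synopsis means embolisation of one lobe. On that reading everything agrees: 100 mg per vial, one vial per lobe, and at most one vial in each lobe. The term is never defined and its use is not uniform. V.2.7 asks for flow to be maintained in the vessel, in the singular, during the procedure. VI.2 stops the procedure at near-stasis, which is observed in the artery being injected. V.2.7 also treats embolisation of each lobe as something that can take place within a session. The comparison of V.2.6 with section VII is not conclusive either, since a check before a bilobar session also precedes the embolisation of each lobe. The text also appears to be translated (SAP 4.2 still contains French), so weight on a single noun should be limited.

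This establishes that a per-lobe intention is possible. It does not remove the inconsistency. Most uses of the word in V.2.6 and V.2.7 describe the whole session, and most of the stopping reasons in VI.2 (failed catheterisation, arterial dissection, anaphylactic shock) fit a session as well. The synopsis applies its limit without a qualifier immediately before a schedule that includes bilobar patients. A stated maximum needs its unit.

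A second reply is that V.2.1 and V.2.7 are clear and agree with each other, so sites would follow them. That may be so, but the documents reviewed contain no rule giving the body precedence over the synopsis.

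**Conclusion.** The concern holds. As written, the synopsis maximum and the V.2.1/V.2.7 dose differ by a factor of 2.0 for bilobar disease treated in one session: 100 mg against a full planned 200 mg. The conflict is confined to session totals above 100 mg and up to 200 mg.

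The conclusion rests on reading *procedure* as the session, which is the protocol's predominant usage but not a defined one. The documents do not say how many bilobar patients would be treated in one session, and they do not show that any site would dose from the synopsis alone. The V.1 treatment figure and the bead-loading instructions mentioned in V.2.3 were not available for this review. The practical effect is therefore unknown.

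The sample size, decision rule and primary analysis are untouched, and no error in the SAP is claimed. SAP 7.5.1 describes the irinotecan dose given and the causes of incomplete administration, so that description will also benefit from a single reference dose per session.

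**What to change.** Reconcile the synopsis with V.2.1 and V.2.7 so that one dose limit appears throughout, with its unit stated both per lobe and per session. Which figure applies is for the sponsor's clinical team; no view is taken here. The cost is one clarifying sentence in a protocol amendment. No SAP change is required.
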